The Effects of Operating Room Virtual Tour on Preoperative Anxiety, Emergence Delirium and Postoperative Behavioral Changes of Pediatric Patients: Prospective, Randomized, and Controlled Trial

NCT number: NCT03172182

Updated date: 01/09/2018

Study

The protocol of this prospective, randomized and controlled clinical trial was approved by the institutional review board of Seoul National University Bundang Hospital (B-1705-396-302) and registered at Clinical Trials Registry (registration number NCT 03172182, <https://clinicaltrials.gov>). All children and parents/guardians received appropriate explanation of this study prior to admission. Written informed consent was obtained from parents/guardians of all children, and assent was also obtained from children older than the age of 7 years. This study was performed at Seoul National University Bundang Hospital, between June and October of 2017.

Virtual reality tour of the operating theater

The 4-min video of the VR tour, a 360° movie, introduced and explained the perioperative preparation process. In this video, Pororo, the famous little penguin character, acts as a pediatric patient who is scheduled be on a tour of the operating theater before surgery. After admission, Pororo changes into a theater gown and intravenous catheter is placed in his forearm. Then, he is transported to the operating theater after confirming his identity in the reception area of the operating theater. Monitoring devices, including ECG, non-invasive blood pressure cuff and pulse oximeter are placed. A facial mask is applied for induction of general anesthesia. During the tour, Pororo explains the preoperative procedure in detail and emphasized that all children can undergo this same process without difficulty.

The script of the VR video was written by an anesthesiologist from Seoul National University Bundang Hospital, and doctors and nurses of this hospital acted in the movie, wearing costumes of animation characters. The VR video was produced in collaboration with

IONIX (Seongnam, Korea) and VR producing company (The VR Co, Seoul, Korea). Seoul National University Bundang Hospital signed a memorandum of understanding with ICONIX to use the animation character Pororo and other characters from the animated film 'Pororo The Little Penguin' (©ICONIX/OCON/EBS/SKBroadband). Filming was carried out using three adapted GoPro Hero4® VR cameras (GoPro, San Mateo, California, USA) by a professional VR company (The VR Co.) in the operating theater of the hospital. The video was then turned into an application for mobile devices. The VR tour was provided using smartphones (Galaxy S6®; Samsung, Suwon, Korea) and VR headsets (VR Gear®; Samsung).

Patients

A total of 86 children, aged 4-10 years with the American Society of Anesthesiologist (ASA) physical status of I or II, undergoing general anesthesia and elective surgery were enrolled for this study. The exclusion criteria included the following: children requiring major surgery or postoperative intensive care; those with a history of prematurity or congenital disease; those with hearing impairment; those with cognitive deficits or cognitive and intellectual developmental disabilities; those who had an experience of anesthesia previously; those taking psychoactive medications; and those with a history of epilepsy or seizure.

Randomization

Randomization was conducted by an independent anesthesiologist who was in charge of patient allocation at 2 h prior to arrival at the preoperative reception area of the operating theater. A computer-generated randomized code (Random Allocation Software version 1.0; University of Medical Sciences, Isfahan, Iran) with nontransparent envelopes that contained sequential

numbers was used. The allocation ratio was 1: 1. The outcome assessor and an anesthesiologist were blinded to group assignment, although children and their parents/guardians were not blinded.

Intervention

Enrolled children were randomly assigned into either the control (n = 43) or VR group (n = 43), and the intervention was done by a researcher in a separate empty room 1 h prior to entering the operating theater to exclude any possible external interferences. Children and parents/guardians in the control group received conventional informative education regarding the perioperative process. Those in the VR group received a VR-guided tour of the operating theater via a smartphone application with a VR headset. After the intervention, an anesthesiologist asked each child and accompanying parent/guardian if they had any questions regarding the perioperative procedures.

Anesthesia

Children were transported from the pre-anesthetic reception are to the operating theater accompanied by their parent/guardian without premedication. Induction of anesthesia was performed by an anesthesiologist with at least 2 years of experience. Standard monitoring devices, including ECG, non-invasive blood pressure cuff, and pulse oximeter, were placed; 5 mg/kg thiopental sodium was administered intravenously while oxygenation was carried out using a facial mask. Upon confirming the disappearance of the eyelid reflex, parent/guardian was guided to the waiting room. Mask ventilation with sevoflurane in oxygen (5 l/min) in increments was commenced to reach the maximum vaporizer setting within a few breaths, and

rocuronium 0.3–0.6mg/kg was given for endotracheal intubation. Anesthesia was maintained with sevoflurane with medical air in oxygen (fraction of inspired oxygen 0.5). At the end of the operation, sevoflurane was discontinued, and glycopyrrolate and neostigmine were given to reverse the neuromuscular blockade. Children were transferred to the postanesthesia care unit (PACU) after extubation.

Outcomes

The primary outcome was the incidence and degree of ED. The degree of ED was measured using Pediatric Anesthesia Emergence Delirium (PAED) scale (Appendix 1) by the blinded assessor at 5 min after the arrival of PACU.

Secondary outcomes included the preoperative anxiety scores and postoperative behavior disturbances. Preoperative anxiety was measured using the validated Korean version of m-YPAS (Appendix 2) by the blinded single assessor to exclude any interrater biases. The m-YPAS score was evaluated on each child twice: baseline (at the time of admission before the study intervention) and just prior to the induction of anesthesia (when the child was placed on the stretcher for transportation from the bed to the operating theater). Postoperative behavior disturbances were recorded using Post-Hospitalization Behavior Questionnaire for Ambulatory Surgery (PHBQ-AS) (Appendix 3) by calling to their parents/guardians on 1 and 14 days after surgery.

Sample size

Power analyses were undertaken using G*Power 3.1.2 (Heinrich-Heine University,

Düsseldorf, Germany). The sample size of the current study was based on the previous investigation on the emergence delirium. The incidence of emergence delirium of the control group (without intervention) was 40.6%, and the reduction of 30% in the incidence of delirium was considered to be clinically significant. A sample size of 43 children per group was determined with a significance level of 0.05 ($\alpha = 0.05$) and a power of 80 percent ($\beta = 0.20$), allowing for a 10 % dropout rate.

Statistical analysis

All data in this study are presented as the median (interquartile range) or numbers (%). SPSS 21.0 for Windows (IBM, Armonk, New York, USA) was used for all statistical analyses. The test of normal distribution was assessed using Shapiro–Wilk test. Mann–Whitney U test was used for analyses of continuous variables (age, weight, height, induction time, m-YPAS, PAED scale and PHBQ-AS) and χ^2 test was used for categorical variables (gender, ASA physical class and incidence of ED). A full analysis set was used for data analysis. P of less than 0.050 was considered statistically significant.

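### Baseline m-YPAS is collected before the intervention, but no planned analysis uses it when preoperative anxiety is compared between groups

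*Combined protocol and SAP*

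**What the plan says.** Preoperative anxiety appears in the trial's title and is a secondary outcome: "Secondary outcomes included the preoperative anxiety scores and postoperative behavior disturbances" (Outcomes). The same section fixes two measurement times. The first is before treatment: "The m-YPAS score was evaluated on each child twice: baseline (at the time of admission before the study intervention". The second is "just prior to the induction of anesthesia (when the child was placed on the stretcher".

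Under Intervention, "the intervention was done by a researcher in a separate empty room 1 h prior to entering the operating theater". The admission score therefore precedes treatment.

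Under Statistical analysis, m-YPAS is one entry in a list that also holds age, weight and height, all assigned to the same method: the Mann–Whitney "U test was used for analyses of continuous variables (age, weight, height, induction time, m-YPAS, PAED scale and PHBQ-AS". The reporting format is also fixed there: "All data in this study are presented as the median (interquartile range) or numbers" with percentages. The section describes no regression, ANCOVA, rank adjustment or change score. It does not say whether the m-YPAS entry means the baseline score, the pre-induction score or both.

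**The concern.** A pre-randomised-treatment measurement of the outcome itself is usually the most useful covariate a trial has. It cannot be affected by the intervention, so adjusting for it introduces no bias, and whatever part of the final score it predicts is removed from the error variance. Here the measurement exists by design but plays no described part in the outcome comparison.

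If the two scores correlate, the anxiety comparison has less power and a less precise estimate than data already in hand would allow. No between-group difference in anxiety with a confidence interval is planned either, so the size of any effect would have to be inferred from two medians.

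**Working it through.** **Inputs from the documents.** 43 children per group, 1:1 allocation, significance level 0.05 (taken as two-sided; the text does not say), and a sample size "allowing for a 10 % dropout rate". Reducing 43 by 10% gives 43 × 0.9 = 38.7, so 39 per arm is used as the lower case.

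**The plan's own figure.** The 43 per group was derived for delirium incidence, not for m-YPAS. Reading the 30% reduction as absolute (40.6% to 10.6%), with two-sided 0.05, 80% power and a continuity correction, gives 39 per arm; 39 × 1.1 = 42.9, or 43. No power figure for anxiety is stated, so there is none to reproduce.

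**Assumptions.** The documents do not give the m-YPAS SD, the effect size or the baseline-to-final correlation r. Each was varied.

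**Closed form (linear ANCOVA, normal scores).** Relative to the unadjusted comparison, the variance is multiplied by (1 − r²)(1 + 1/(N − 4)). With N = 86 the second term is 1 + 1/82 = 1.012.

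| r | Variance factor | Equivalent n per arm (43 ÷ factor) | Power if unadjusted power is 80% (0.604 SD) |
|---|---|---|---|
| 0 | 1.012 | 42.5 | 79.5% |
| 0.3 | 0.921 | 46.7 | 83.1% |
| 0.5 | 0.759 | 56.6 | 89.5% |
| 0.7 | 0.516 | 83.3 | 97.4% |

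Break-even is where 1 − r² = 82/83, so r = √(1/83) ≈ 0.11.

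**Simulation of the planned test against a rank-based adjusted test.** The adjusted test is Quade's: rank both scores, regress final ranks on baseline ranks, and compare the residuals between groups. There were 20,000 trials per cell, so the Monte Carlo standard error near 60% is √(0.6 × 0.4/20,000) ≈ 0.35 points. The five-item score uses the Appendix 2 formula with assumed, floor-skewed item shares: 50/25/15/10% for the four-level items and 45/18/14/10/8/5% for vocalizations. This gives SD 21.4, 24% of children at the minimum of 23.3, and a mean difference of about 9.1 points. Power in %:

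| Setting | Test | r=0 | 0.1 | 0.2 | 0.3 | 0.5 | 0.7 |
|---|---|---|---|---|---|---|---|
| Normal, 43 per arm, 0.5 SD | Mann–Whitney | 60.4 | 60.4 | 60.6 | 60.7 | 60.0 | 61.2 |
| | Quade | 60.1 | 60.6 | 61.9 | 64.1 | 71.1 | 86.1 |
| Normal, 39 per arm, 0.5 SD | Mann–Whitney | 56.5 | 56.3 | 56.8 | 56.7 | 56.7 | 56.6 |
| | Quade | 56.3 | 56.1 | 58.0 | 60.1 | 67.3 | 81.6 |
| Normal, 43 per arm, 0.3 SD | Mann–Whitney | 26.9 | 27.1 | 26.5 | 26.3 | 27.1 | 26.4 |
| | Quade | 26.9 | 27.2 | 27.4 | 28.4 | 32.9 | 44.0 |
| Five-item score, 43 per arm | Mann–Whitney | 60.6 | 60.7 | 60.8 | 60.7 | 60.5 | 61.7 |
| | Quade | 60.4 | 60.7 | 61.9 | 64.2 | 71.6 | 85.3 |
| | Plain ANCOVA | 57.8 | 58.6 | 59.6 | 61.6 | 69.7 | 85.1 |

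Hand check of the first row, using the Mann–Whitney relative efficiency of 0.955: Φ(0.5 × √(43 × 0.955/2) − 1.96) = Φ(0.31) ≈ 62%, close to the simulated 60–61%.

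Type I error was 4.7–5.2% for Mann–Whitney and 4.8–5.2% for Quade.

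**Interval width.** For the five-item score (8,000 trials), the baseline-adjusted difference with an HC3 robust 95% CI had coverage of 95.0–95.3%. Its mean width was 16.9, 16.2, 14.8 and 12.3 points at r = 0, 0.3, 0.5 and 0.7, against 16.5 unadjusted. As ratios these are 1.02, 0.98, 0.90 and 0.75.

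**Would a change score do instead?** Its variance factor is 2(1 − r), which exceeds 1 whenever r is below 0.5. It exceeds the large-sample ANCOVA factor at every r below 1, because 2(1 − r) − (1 − r²) = (1 − r)². In simulation (43 per arm, 0.5 SD), Mann–Whitney on change had 34%, 47%, 60% and 82% power at r = 0, 0.3, 0.5 and 0.7, below Quade throughout.

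**The case against.** The strongest reply is that nothing here is wrong. Randomization already protects the comparison from bias, an unadjusted rank test is a legitimate choice for a bounded ordinal score, and the outcome is secondary. All of that stands.

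The benefit also depends on a correlation the documents do not supply. The two scores are taken in different settings, with an intervention and an unstated interval between them, so r could be low. A calmer baseline shrinks the gain: with about 62% of children at the floor, nominal correlations of 0.3, 0.5 and 0.7 became observed rank correlations of 0.22, 0.37 and 0.52. Quade power was then 62%, 67% and 76%, against 61%, 62% and 60% for Mann–Whitney. This stands as a limit on the size of the gain. Adjustment still did no harm.

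Two points of wording also stand in part. The m-YPAS entry may cover a baseline comparison between groups, so baseline is unused only in the sense that no described outcome comparison draws on it. And the claim of no statistical cost fits the rank test; the raw-scale interval is slightly wider at r = 0.

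Finally, the document is dated 01/09/2018 and the study ran from June to October 2017, so the addition may have to be post hoc. That limits the weight an adjusted result can carry, but does not make it uninformative.

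**Conclusion.** The concern holds, as an available improvement to a valid analysis of a secondary outcome. The plan describes no use of the pre-intervention m-YPAS in the anxiety comparison and does not name the score being compared.

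Under the assumed effects and score distributions in the table, the power gain from rank-based adjustment is nil within simulation error at r of 0–0.1 and about 1 to 3.5 points at r of 0.2–0.3. At r = 0.5 it is about 6 to 11 points, and at r = 0.7 about 18 to 25 points. The true r is unknown, and a heavy floor at baseline would pull these gains down. Because the rank form loses essentially nothing even at r = 0, the case for it does not depend on r being high. Plain ANCOVA is less safe as the test: on the skewed score it falls slightly below Mann–Whitney at r of 0.2 or less.

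The change is worth making but alters no conclusion about delirium. Confidence is medium, because the benefit rests on quantities the documents do not report.

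**What to change.** 1. State in one line that the pre-induction m-YPAS is the score compared between groups.
2. Keep the Mann–Whitney test on that score and report beside it a baseline-adjusted comparison by rank-based ANCOVA, for example Quade's method.
3. Add a baseline-adjusted difference on the m-YPAS scale with a 95% CI, from ANCOVA with a robust or bootstrap interval. The rank test and this interval address different quantities, so say that the interval describes the size of the effect and the rank test supplies the adjusted p-value.
4. Give the date on which the adjusted analysis was added. It may be the main anxiety analysis only if it was fixed before unblinded data were seen. Otherwise label it post hoc and supportive, with Mann–Whitney remaining the main comparison.

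The cost is small: no new data and no change to the sample size. Both scores are already collected, and ranking, regression and residual comparison are standard procedures in general statistical software such as the SPSS version that, by the plan, "was used for all statistical analyses".

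### The primary ED and PAED comparisons are valid but unadjusted; adjusting for age and baseline m-YPAS, both already recorded, could gain precision at almost no cost

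*Combined protocol and SAP*

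**What the plan says.** The Outcomes section makes the incidence and the degree of ED the primary outcome, with degree measured on the PAED scale. It has m-YPAS scored twice, the first time at admission before the intervention.

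The Statistical analysis section gives one test per variable type. The Mann–Whitney U test "was used for analyses of continuous variables (age, weight, height, induction time, m-YPAS, PAED scale and PHBQ-AS"). The chi-square "test was used for categorical variables (gender, ASA physical class and incidence of ED"). Age and m-YPAS therefore appear only as variables to be compared between arms. No regression, ANCOVA or stratified test is planned.

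The Patients section states "A total of 86 children, aged 4-10 years". The Randomization section states "The allocation ratio was 1: 1" and describes a computer-generated code in opaque envelopes, with no mention of stratification.

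**The concern.** The trial is small, the age range is wide for this kind of behavioural outcome, and allocation is not described as stratified. Two covariates that the intervention cannot have affected are already in the data. If either predicts ED or PAED, leaving it out keeps explainable variation in the error term, and the treatment effect is estimated less precisely than these data allow. Comparing age between arms with a P value does nothing for the precision of the treatment comparison.

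What is at stake is the width of the confidence interval and some power, not the validity of the result.

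**Working it through.** **1. The plan's own figure.** Inputs from the Sample size section: "The incidence of emergence delirium of the control group (without intervention) was 40.6" per cent, a 30% reduction, "with a significance level of 0.05", "a power of 80 percent" and 10% dropout. A two-sided test is assumed, since sidedness is not stated. Read as an absolute reduction, the VR rate is 40.6% − 30% = 10.6%.

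- Uncorrected chi-square: n = [1.960 × √(2 × 0.256 × 0.744) + 0.842 × √(0.406 × 0.594 + 0.106 × 0.894)]² / 0.30² = 32.0, so 33 per group.
- With continuity correction: (32.0/4) × [1 + √(1 + 4/(32.0 × 0.30))]² = 38.4, so 39 per group.
- With dropout: 39 × 1.1 = 42.9, so 43; or 39/0.9 = 43.3, so 44.

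The stated 43 per group is reproduced from an unadjusted comparison. A relative 30% reduction (to 28.4%) would need 238 to 255 per group before dropout, so only the absolute reading fits.

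**2. PAED, adjusting for two covariates.** The document gives no correlation, so R² is an assumed range. In a linear approximation with N = 86 and k = 2, the variance ratio (adjusted to unadjusted) is (1 − R²) × (N − 3)/(N − k − 3) = (1 − R²) × 83/81. The last column is Φ((1.960 + 0.842)/√ratio − 1.960), the power after adjustment of a comparison that has 80% without it.

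| R² (assumed) | Variance ratio | Power |
|---|---|---|
| 0 | 1.025 | 79% |
| 0.05 | 0.973 | 81% |
| 0.10 | 0.922 | 83% |
| 0.20 | 0.820 | 87% |
| 0.30 | 0.717 | 91% |

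Break-even is at R² = 1 − 81/83 = 0.024.

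A simulation of the tests themselves agrees (43 per arm; PAED SD 5 and a 3-point shift, both assumed). Mann–Whitney against rank ANCOVA on both covariates gives power of 76.5% vs 76.2% with no correlation, 75.7% vs 78.4% with both correlations 0.2, and 75.5% vs 82.4% with both 0.3. Type I error stays near 5%.

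**3. ED incidence.** Simulation at 43 per arm, 4,000 runs per scenario, chi-square against logistic adjustment. R² is that in the control arm. The variance ratio is for the standardised risk difference against the raw one. The 20% VR rate is an assumption, showing a smaller effect than planned.

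| R² (assumed) | Variance ratio, 40.6% vs 10.6% | Power, 40.6% vs 10.6% | Power, 40.6% vs 20% |
|---|---|---|---|
| 0 | 1.02 | 91.2% vs 91.4% | 56.8% vs 56.9% |
| 0.05 | 1.00 | 91.9% vs 92.8% | 56.3% vs 58.6% |
| 0.17 | 0.90 | 92.6% vs 95.3% | 55.0% vs 62.4% |
| 0.29 | 0.82 | 92.3% vs 96.8% | 56.8% vs 69.0% |

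The gain is smaller than for PAED: at R² = 0.17 the PAED ratio is 0.83 × 83/81 = 0.85, against 0.90 here. With no effect (40.6% in both arms), rejection rates were 5.2–5.8% for chi-square and 4.8–6.2% for the adjusted test, so very small power differences should not be read closely.

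**4. Room in the logistic model.** Expected events at the planned rates: 43 × 0.406 + 43 × 0.106 = 17.5 + 4.6 = 22. That supports group plus two covariates, and no more.

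**5. Size of a chance age gap.** With ages even over 4 to 10 (assumed), the SD is 6/√12 = 1.73 years. The SE of the difference in mean age is 1.73 × √(2/43) = 0.37 years, so gaps up to about 1.96 × 0.37 = 0.73 years are ordinary. At an assumed age–PAED correlation of 0.3 and SD 5, a 0.7-year gap shifts PAED by 0.3 × (5/1.73) × 0.7 = 0.6 points. The SE of the PAED difference is 5 × √(2/43) = 1.1 points.

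**The case against.** The strongest reply is that nothing here is wrong. Mann–Whitney and chi-square are valid in a 1:1 randomised trial, need no model, and match the comparison on which the sample size was planned. This stands, and it limits the point to efficiency.

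A reader might infer three stronger things.

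- *That the plan gives up precision.* The documents do not show this. It depends on how prognostic age and baseline m-YPAS are, and no figure is given. Below R² of about 0.024 for PAED, adjustment costs slightly more than it returns.
- *That adjustment is free.* It is nearly so. Two covariates spend two degrees of freedom, worth 2.5% of variance or about one point of power if they predict nothing.
- *That chance age imbalance distorts the result.* The P values of the unadjusted tests already allow for chance imbalance, and the 0.6-point shift in step 5 is inside the 1.1-point SE.

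Timing also matters. The protocol says the study ran from June to October 2017, and the document is dated 01/09/2018. Covariates added now may not count as pre-specified. This stands too; it affects how the adjusted analysis should be labelled, not whether it is informative.

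**Conclusion.** The point holds as an optional efficiency improvement. Both primary comparisons ignore two covariates recorded before the intervention. Adjusting could reduce PAED variance by about 8% at R² = 0.10 and 18% at R² = 0.20, against a loss of 2.5% if neither covariate is prognostic. For ED incidence the reduction is about 10% at R² = 0.17 and nil at 0.05. At the planned ED effect the unadjusted test already has power above 90% with all 43 per arm, so the gain would matter mainly for PAED or for a smaller ED effect.

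These figures rest on assumed R² values, a linear approximation for PAED, and assumed SD, shift and age distribution in the simulation and the age-gap check. No bias or type I error fault is claimed, and the stated sample size is not in question.

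**What to change.** Add a short paragraph to the Statistical analysis section:

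- PAED: rank ANCOVA, regressing ranked PAED on group, age and baseline m-YPAS.
- ED incidence: logistic regression on group and the same two covariates only, reported as a standardised risk difference with 95% CI.
- Report the Mann–Whitney and chi-square results alongside.
- Describe baseline characteristics by arm without P values.
- Fix the covariates before outcomes are seen by arm. If they have already been seen, keep the unadjusted tests as the main analysis and label the adjusted one a sensitivity analysis.

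The cost is a few lines of text and code, two degrees of freedom and a sentence of explanation in the report. No new data are needed.
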